5.3 Adherence to allocated interventions and intervention fidelity

The intervention characteristics will be described for both the control and intervention conditions. Fidelity assessment of the classroom sessions will be additionally arrived from ratings provided by an independent intervention coordinator for 20% of the classes in the trial intervention.

Time	School ba	Classroor	n sen	sitization						
neriod								sessions		STELEGENOT
penou	Posters	Drop- box	School Prir	ncipal & Tea	acher meet	ings		303310113		
				•						
	Ν	N	Number of School Principal meetings (N)	Duration of the Principal Meetings (min)	Number of Teacher meetings (N)	Number of teachers participated in meeting (N, % of total teachers)	Duration of the teacher meetings (min)	Number of sessions (N)	Number of students attended the session (N, % of total)	Fidelity rating Mean (SD)
Period										
1:										
Period 2:		.				.	.			
Period 3:										

Table 4: Intervention delivery across the school-based and classroom-based sensitization sessions

6. Outcome analysis

6.1 Summary of referrals across the two conditions

The numbers and proportion of students referred from each class across the intervention and control conditions will be summarised along with pertinent contextual factors. Similarly, number and proportion of these referrals referred through each of the different sources, and the number, and proportion of the students eligible to receive problem solving intervention across the control and intervention conditions will be summarised through tables/ graphs. The severity of mental health symptoms and the scores internalising and externalising symptom sub-types will also be presented across the two conditions.

6.2 Analysis of primary outcome

In this section, we describe the statistical analysis for the primary outcome. The intervention delivery in the intervention condition at class level (cluster). As we know the size of classes and have the data for all the referred students in each of the time periods, we are able to construct the data at the individual level:

$$Y_{ijk} = \begin{cases} 1 & if \ student_{ijk} \ referred \\ 0 & else \end{cases}$$

where i = 0 or 1 (0 = control condition, 1 = intervention condition), $j = 1, ..., m_i$ (number of classes in each condition), $k = 1, ..., n_{ij}$ the number of students in class j in condition i. We therefore have observations nested within students and students nested within classes. The primary analysis takes data of all three time periods into account. So, we have

$$Y_{ijkl} = \begin{cases} 1 & if \ student_{ijk} \ referred \ in \ period \ l \\ 0 & else \end{cases}$$

where l = 1, 2 or 3 to indicate the period.

Figure 3: Trial schematic indicating the effects that can be measured (adapted from figure 1)

		Step 1	Step 2
Sequence 1 (1-35 classes)	Control condition (immediate control effect)	Intervention condition (immediate intervention effect)	Intervention condition (continued intervention effect)
Sequence 2 (36-70 classes)	Control condition (immediate control effect)	Control condition (continued control effect)	Intervention condition (immediate intervention effect)
Time	1 st time period (4 weeks)	2 nd time period (4 weeks)	3 rd time period (4 weeks)

We can describe the following effects of the intervention (figure 3):

- The classes in sequence 1 and sequence 2 underwent the immediate effect of the school level sensitization intervention (control condition) at the first period.
- The classes in sequence 1 and sequence 2 underwent immediate effects of receiving classroom sensitization intervention (intervention condition) in the second and third time periods respectively the main parameter of interest.
- The classes in sequence 2 underwent continued effects of receiving school level sensitization intervention (control condition) in second time period.
- The classes in the sequence 1 underwent continued effects of receiving the classroom sensitization intervention (intervention condition) in the third time period.

These effects can be described in the following equation

$$logit\left(P(Y_{ijkl})\right) = \theta_0 + \theta_1 X_{li} + \theta_2 T_{2l} + \theta_3 T_{3l}$$

Where:

 Y_{ijkl} is as before, $logit(P(Y_{ijkl}))$ is the log odds of being referred to the counselling program

 θ_0 is a constant that reflects the immediate effect of school-level activities (for all classes in first time period),

 θ_1 reflects the immediate effect of the classroom activities and is the main parameter of interest (corresponding to the classes receiving the classroom intervention - classes of sequence 1 in the second time period and classes of sequence 2 in the third time period),

 θ_2 reflects the continued effects of the school-level activities (corresponding to the sequence 2 classes continuing in the control condition in second time period),

 θ_3 reflects the continued effect of the classroom activities (corresponding to the classes of sequence 1 continuing in the intervention condition in the third time period)

 X_{li} is an indicator for the time periods when classroom intervention in introduced (equals 1 if i = 1 and l = 2 (sequence 1 classes that received classroom intervention at period 2) or if i = 1 and l = 3 (sequence 2 classes that received classroom intervention at period 3)),

 T_{2l} is an indicator for second time period where classes of sequence 2 experienced continued effect of school sensitization activities (equals 1 if i = 0 and l = 2),

 T_{3l} is an indicator for the third time period where classes of sequence 1 experienced continued effects of the classroom sensitization intervention (equals 1 if i = 0 and l = 3)

We have data with three records for each student, for time period 1, 2 and 3, with students nested in classes. The calculation of the parameters will need to account for this clustering of data at the class level. Analysis will be undertaken using Generalized Estimating Equations (GEE) with robust standard errors that are measured using the sandwich estimator method. GEE is a general statistical approach to fit a marginal model for longitudinal/ clustered data analysis. GEE was introduced by K. Liang and S. Zeger(13) to analyse longitudinal data without resorting to fully specified random effect models and can be applied to both continuous and categorical outcomes. It is a recommended method for analysis of the stepped wedge cluster randomised controlled trials(14), and provides population averaged effects of exposure to the interventions across the control and intervention conditions. GEE provides both parameter estimates and standard errors that are corrected for clustering of data and are consistent despite misspecifications in the correlation structure. For these reasons, GEE is a suitable method for analysis of primary outcome in this trial.

The analysis will be carried out using "xtgee" command using Stata 15.1. The panel structure of data and clustering of data at class level will be specified through stata command "xtset". The following will be specified in the GEE model:

- Family of distribution of the response variable: Binomial as the outcome variable is binary.
- Link function: Logit link function.
- The within-group correlation structure will be specified as independent.
- Standard error type: robust.

Having a variable for indicating the class in which student observations are nested (class_id), outcome variable indicating the referral status of the adolescent (referred), time indicator (t2) for period 2 for classes that continue to experience school based sensitization activities, indicators for the immediate and continued effects of classroom sensitization activities (effect_lag0 and effect_lag1), the parameters will be estimated using the stata command as illustrated below:

"xtset class_id"

"xtgee referred t2 effect_lag0 effect_lag1, family(binomial) link(logit) corr(independent) vce(robust)"

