The trial aims to evaluate the impact of a one-off classroom-level information and engagement session conducted by a 'lay' counsellor as compared to school-level sensitization activities on the demand for school counselling program among adolescents in government-run secondary schools in New Delhi, India. This trial is part of a larger research program called PRIDE (PRemlum for aDolEscents) whose overall goal is to develop and evaluate a trans-diagnostic, stepped-care intervention targeting common mental disorders in school-going adolescents in India. The PRIDE intervention architecture involves two sequential psychological treatments of incremental intensity. The first step is a brief problem-solving intervention delivered by lay counsellors. Adolescents with enduring mental health problems are referred to a higher intensity trans-diagnostic treatment delivered by psychologists. The trial described here is embedded within a trial testing the effectiveness of the low-intensity problem-solving intervention (host trial). The trial protocols for both these trials are elaborated in a journal publication(1). The trial is registered prospectively on ClinicalTrials.gov/ct2/show/NCT03633916 (available at: https://clinicaltrials.gov/ct2/show/NCT03633916).

3. Objectives and Hypothesis

The primary objective of this stepped-wedge, cluster randomised controlled trial is to evaluate the impact of a classroom sensitization session (intervention condition), over and above school-level sensitization activities (control condition), on the rate of referred adolescents (i.e. the proportion of adolescents referred as a function of the total sampling frame in each condition) into the host trial.

The secondary objectives are:

- To evaluate the proportion of such referrals meeting the eligibility criteria of the host trial across the control and intervention conditions
- To evaluate the proportion of such referrals that are self-referrals across the control and intervention conditions
- To explore the severity of mental health symptoms reported by referred adolescents across the control and intervention conditions
- To explore the symptom sub-types (internalising and externalising symptoms) reported by referred adolescents across the control and intervention conditions

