3.6 Power calculation

We based our power calculation on a within-period comparison for a stepped wedge design(10), using Stata package "clustersampsi". Based on pilot data, we anticipated referral rates of 5% and 15% on the control and intervention conditions respectively, with an intra-cluster correlation coefficient (ICC) of 0.124. We assumed the same ICC for the between-time correlation given the short time period of follow-up. In practice, it may be smaller than 0.124 and both ICCs will be reported. Using these parameters, a sample size of 70 classes (average class size of 50 students) will have 92% power to detect a difference of 10 percentage points (treating the outcome as a binomial variable), at a significance level of 0.05.

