6.4 Sensitivity analysis

The sensitivity analyses is based on the methods described in Thompson et al, 2018 (10) which is also used for calculating the power of the study. It uses data from the 2nd period only, since it is in this period where the two conditions differ most transparently: sensitization intervention versus no sensitization intervention. We will use GEE method to arrive at population averaged estimates of the effects of exposure to the interventions across the control and intervention conditions. As the power calculation for this trial is based on this method, we will assess the robustness of the results obtained by the primary method of analysis using this method.

To estimate the intervention effect, we need to estimate the parameters in the following regression equation

$$logit(P(Y_{ijkl})) = \mu + \theta X_i$$

where Y_{ijkl} is as before, μ is a constant, θ is the parameter of interest (the population-averaged estimate of the effect of the intervention), X_i is in indicator variable ($X_i = 0$ for the control condition and $X_i = 1$ for the intervention condition).

A separate file with a sub-set of data with all observations pertaining to time period 2 will be created for the analysis. Having data with one record for each student, and a variable to indicate the class in which the observations are nested (class_id), an indicator for being assigned to the intervention condition (intervention) and an indicator for the outcome variable of being referred (referred), the following stata commands will be used to analyse the intervention effect in period 2. We will first specify the panel data structure with clustering of data at class level using the command "xtset" and then specify the GEE model through the stata command "xtgee".

"xtset class_id"

STATISTICAL ANALYSIS PLAN FOR THE SENSITIZATION TRIAL

"xtgee referred intervention, family(binomial) link(logit) corr(independent) vce(robust)"

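### The primary parameter theta1 compares later periods with period 1 and leaves out the randomised period-2 control data, so any change in referrals over time is counted as intervention effect

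*SAP*

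**What the plan says.** All 70 classes are in the control condition in period 1. Sequence 1 receives the session in period 2 and sequence 2 in period 3 (SAP section 3.1). The primary objective in section 3 is the effect of the session "over and above school-level sensitization activities (control condition".

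Section 6.2 sets up four parameters:

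- The reference level is theta0, which "is a constant that reflects the immediate effect of school-level activities (for all classes in first time period".
- The coefficient for sequence 1 in period 2 and for sequence 2 in period 3 is theta1. The SAP says that it "reflects the immediate effect of the classroom activities and is the main parameter of interest".
- A separate coefficient, theta2, by the SAP's account "reflects the continued effects of the school-level activities (corresponding to the sequence 2 classes continuing in the control condition in second time period".
- The last one, theta3, covers sequence 1 in period 3. Its indicator is described as marking classes that "experienced continued effects of the classroom sensitization intervention (equals 1 if i = 0 and l = 3".

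The command has the same three terms: "xtgee referred t2 effect_lag0 effect_lag1, family(binomial) link(logit) corr(independent) vce(robust". The accompanying text describes `t2` as marking period 2 only for classes still in control.

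The concurrent comparison in period 2 appears in section 6.4 as the sensitivity analysis, with the reason: "It uses data from the 2nd period only, since it is in this period where the two conditions differ most transparently". Section 3.6 bases the power calculation on that within-period comparison.

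**The concern.** In a stepped-wedge trial condition and calendar time are confounded by design: every class is in control first and in intervention later. The analysis separates them by comparing classes in different conditions in the same period. Here only period 2 offers that comparison, since all classes are in control in period 1 and none are in period 3.

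Neither the equation nor the command contains a period effect common to both sequences. If the period-2 control classes have a free parameter of their own, they cannot inform theta1, and theta1 is judged against period 1 alone. A launch surge that fades after the first posters and teacher meetings, exam-related demand, depletion of students already referred, or growing familiarity with the service would then enter theta1. The main result could show an effect that is absent or miss one that is real.

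The plan's own parameters point the same way. It lets school-only referrals in period 2 differ from period 1 (theta2), so the period-2 effect over control is theta1 - theta2. Yet theta1 is the quantity to be reported.

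**Working it through.** **Inputs.** From section 3.6: 70 classes of 50 students, referral 5% versus 15%, ICC 0.124 within and between periods, power 92%, "at a significance level of 0.05" (taken as two-sided). From section 3.1: 35 classes per sequence. From section 6.2: the indicators, logit link, independence working correlation and robust standard errors. The time trends below are assumptions, because the SAP gives none.

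**1. The plan's power figure.** Design effect = 1 + 49 × 0.124 = 7.076. Effective n per arm = 35 × 50 / 7.076 = 247.3.

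z = (0.10 - 1.96 × √(2 × 0.10 × 0.90 / 247.3)) / √((0.05 × 0.95 + 0.15 × 0.85) / 247.3) = (0.10 - 0.0529) / 0.0266 = 1.77

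This is a power of 96.2%, against 92% stated. A power near 92% appears only with inputs the SAP does not state, such as a class-size coefficient of variation near 0.5. The gap does not affect this point. It shows only that the period-2 comparison is adequately powered.

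**2. What theta1 estimates.** Log odds by cell, from the section 6.2 indicators:

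| | Period 1 | Period 2 | Period 3 |
|---|---|---|---|
| Sequence 1 | theta0 | theta0 + theta1 | theta0 + theta3 |
| Sequence 2 | theta0 | theta0 + theta2 | theta0 + theta1 |

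The six cells form four free groups. Under independence GEE each group is fitted by its pooled rate, so

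theta1 = logit(pooled rate of sequence 1 period 2 and sequence 2 period 3) - logit(period-1 rate).

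Sequence 2 in period 2 enters only theta2.

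**3. Check.** Hold period 1 at 5% and the two first-exposure cells at 15%, and vary the period-2 control rate:

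| Period-2 control rate | exp(theta1) | Period-2 concurrent odds ratio |
|---|---|---|
| 1% | 3.35 | 17.5 |
| 5% | 3.35 | 3.35 |
| 15% | 3.35 | 1.00 |
| 50% | 3.35 | 0.18 |

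When session and control classes do equally well in the same weeks (15% each), the primary analysis still reports 3.35.

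**4. No true effect, assumed trend.** For 5/6/7% over periods 1 to 3 the pooled rate is 6.5%, and the odds ratio is (0.065/0.935) / (0.05/0.95) = 1.32. The other rows follow in the same way. Rejection rates come from 2,000 simulated trials per row, with the SAP's equal between-period ICC modelled as fully stable class effects:

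| Background rates | exp(theta1) | theta1 significant | Period-2 contrast significant |
|---|---|---|---|
| 5/5/5% | 1.00 | 6% | 6% |
| 5/6/7% | 1.32 | 80% | 7% |
| 5/7.5/10% | 1.82 | 100% | 6% |
| 5/4/3% | 0.69 | 88% | 8% |
| 5/3/2% | 0.49 | 100% | 7% |

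The rejection rate depends on how stable class effects are over time; the bias does not. For a step from 5% to 7%, the odds ratio is (0.07/0.93) / (0.05/0.95) = 1.43. Simulation rejects in 94-96% of trials at class-effect correlation 1.0, 51-54% at 0.7 and 37% at 0.4. For a step from 5% to 6%, the odds ratio is 1.21 and rejection is 52%, 19% and 14%.

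**5. True within-period odds ratio 3.35, assumed trend.** A 5/7.5/10% background gives exp(theta1) = 6.09, and 5/3/2% gives 1.63. If school-only referrals fade from 5% to 1.5%, the session odds are 3.35 × 0.015/0.985 = 0.0510, and exp(theta1) = 0.0510 / (0.05/0.95) = 0.97.

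**6. Other readings of the text.** Taken literally with i as condition, no cell has i = 0 in period 3. The third indicator is then always zero and X covers all of period 3. theta1 is still set against period 1 only, with odds ratio 1.36 under 5/6/7% and no effect. If `t2` marked period 2 for all classes, against its description, the odds ratio would be 1.23 with 55% rejection. Neither reading removes the bias.

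**The case against.** The strongest reply is that the contrast looks deliberate. Figure 3 labels period 1 as the immediate control effect and theta1 as the immediate intervention effect, so the first four weeks of one activity are set against the first four weeks of the other. On that view the fading-launch example (odds ratio 0.97) is a different estimand correctly estimated. This has some force for that example. It does not answer calendar drift, and it does not fit an objective stated as the gain beyond school-level activities.

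Second, section 6.4 already specifies the randomised period-2 contrast, and theta2 would show any movement in control referrals. So the valid analysis exists. But it is only a sensitivity analysis, and no rule says what to conclude if it disagrees with theta1.

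Third, the trend sizes are assumed, and the highest rejection rates need fully stable class effects, while section 3.6 concedes that the between-period ICC may be smaller. That stands, which is why ranges are shown. With no trend at all theta1 is unbiased, but the plan does not assume this and theta2 allows the opposite.

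Fourth, sequence 2 does contribute to theta1, through its period-1 and period-3 records. Only its period-2 records are lost, but those are the concurrent controls.

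Finally, the index errors in X and T3 are drafting slips: the words beside them fix the intended cells. They need correcting but add no weight.

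**Conclusion.** The concern holds. As defined and coded in section 6.2, theta1 is a before-after contrast with period 1, and the only randomised concurrent control cell has no influence on it. That follows algebraically from the SAP's own indicators under independence GEE and needs no assumption about trends. It conflicts with the primary objective and with the within-period basis of the power calculation.

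The size of the error depends on the trend, which is unknown. With no true effect, a step from 5% to 7% yields an odds ratio of about 1.43 and false significance in roughly 37% to 96% of trials, depending on the between-period correlation. Falling referrals bias the result the other way. The period-2 contrast stays at odds ratio 1.00 in all these null scenarios and rejects in 6-8% of trials. This should be corrected before the primary analysis is run.

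**What to change.** Make the period-2 comparison of section 6.4 the primary analysis. Equivalently, fit period indicators for all classes and report `effect_lag0`:

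`xtgee referred i.period effect_lag0 effect_lag1, family(binomial) link(logit) corr(independent) vce(robust)`

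Under independence this coefficient equals logit(sequence 1, period 2) - logit(sequence 2, period 2). Keep the present theta1 only as a before-after description, labelled as such, and state that the concurrent contrast governs if the two differ. Correct the index definitions of X and T3 to match the code.

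Section 6.3 reuses the same model and needs the same period terms. Precision there is untested. At 5% referral the period-2 controls yield about 35 × 50 × 0.05 = 88 referred students, and a comparison among referred students is not protected by randomisation even within one period.

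The cost is SAP wording and one line of code, with no new data. The interval widens: at 5% versus 15% the standard error of the log odds ratio is about 0.33, against 0.12 to 0.21 for theta1, so it is about 1.6 to 2.8 times as wide. Simulated power is about 96% without a trend. With a true odds ratio of 3.35 it is 91% if background referrals fall 5/4/3% and 84% if they fall 5/3/2%. Because the sandwich standard error rejects slightly too often, a small-sample correction could be specified in the same revision.

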3.1 Trial Design

The trial will be implemented as a Stepped Wedge Cluster Randomised Controlled Trial (SW-CRCT). The essential feature of a SW-CRCT is that random allocation determines the time period in which clusters begin an intervention. All clusters start with the first time period of control intervention, and cross-over from the control to the intervention condition across pre-defined time periods, in a random, but sequential, order(4).

We will select 70 classes using stratified randomisation to represent each of the grades 9th, 10th, 11th, 12th across the six participating schools in Delhi with probability proportional to size.

		Step 1	Step 2	Sequence of receiving treatments*
Sequence 1 (1-35 classes)	Control condition	Intervention condition	Intervention condition	011
Sequence 2 (36-70 classes)	Control condition	Control condition	Intervention condition	001
Time	1 st time period (4 weeks)	2 nd time period (4 weeks)	3 rd time period (4 weeks)	

Figure 1: Illustration showing implementation of the control and intervention conditions.

Notes: The white boxes indicate the group of classes in the control condition and the coloured boxes indicate the group of classes in the intervention condition. *0=control condition; 1=intervention condition The 70 classes will be randomised to be a part of either of 2 sequences as shown in Figure 1. A small block size of 2 will be used to allocate the 70 classes across the two sequences in order to ensure balance, as the number of classes within each grade from the individual schools is relatively small. In the rare instance that a selected class has been dissolved or merged with another class, the next class in the random list will be included to replace the unavailable class. Each sequence will be implemented over three consecutive 4-week intervals. The trial will be conducted over 12 weeks except for breaks due to exams and holidays. All classes will begin with the control intervention period of 4 weeks, where only school level activities will be rolled out.

Notes: The white boxes indicate the group of classes in the control condition and the coloured boxes indicate the group of classes in the intervention condition.

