- Blocks: As the selected numbers of classes within each school-grade combination is often small, block size of 2 was used to assign the classes to one of the two groups, so that allocation of classes can be balanced across both the treatment groups.
- Creating blocks: 2 classes within the same school and standard were grouped together to form a block. If this was not possible, then classes were clubbed together within the classes from same grade from other schools to form blocks of two.
- Each of the blocks thus created were numbered sequentially from 1-35.
- Randomisation is required to allocate the classes across two sequences:
 - Sequence 1 Group A: 1-35 classes to receive the intervention condition in the second time period.
 - Sequence 2 Group B: 36-70 classes to receive the intervention condition in the third time period.
- The first 17 blocks were labelled AB and subsequent 18 blocks were labelled BA. Using excel command rand() a random number was allocated to each of these blocks. With sorting on random number, AB and BA were randomly allocated to each of the 35 blocks (Table 1.4).
- These classes within each block was then assigned to the treatment group as per the sequence generated in table 1.4. The final list of classes randomised in two groups as per the above process is re-produced in table 1.5, and will be used for the trial.

Table 1.4: Rando	m allocation	of the blocks
------------------	--------------	---------------

Block number for		
randomisation	Blocks	Random number
1	AB	0.997221
2	BA	0.804859
3	AB	0.814548
4	AB	0.773763
5	AB	0.152418
6	BA	0.007255
7	BA	0.356458
8	BA	0.654178
9	AB	0.817778
10	BA	0.212944
11	AB	0.115815
12	AB	0.22788
13	AB	0.673958
14	BA	0.031788
15	AB	0.00872
16	BA	0.298582
17	BA	0.282199
18	AB	0.43279
19	BA	0.716775
20	AB	0.874177
21	AB	0.262606
22	BA	0.936284
23	BA	0.805721
24	BA	0.319226
25	BA	0.24751
26	AB	0.953943
27	BA	0.809131
28	BA	0.609128
29	BA	0.485599
30	BA	0.924817
31	BA	0.28247
32	AB	0.7649
33	AB	0.171817
34	AB	0.636414
35	AB	0.042925

Sequence 1: Group A (Classes 1-35)		5)	Sequence 2: Group B (Classes 36-70)		
School code	Grade	Class	School code	Grade	Class
1	9	1-9-E	1	9	1-9-F
1	9	1-9-H	1	9	1-9-G
1	9	1-9-I	1	9	1-9-К
1	10	1-10-C	1	10	1-10-F
1	10	1-10-E *	1	10	1-10-D *
1	11	1-11-E	1	11	1-11-A
2	9	2-9-B	2	9	2-9-A
2	9	2-9-J	2	9	2-9-G
2	9	2-10-C *	2	10	2-10-В
2	10	2-10-Е	2	11	2-11-D
2	11	2-11-A	2	12	2-12-D
2	12	2-12-C	3	9	3-9-E
3	9	3-9-A	3	9	3-9-G
3	9	3-9-H	3	10	3-10-Е
3	10	3-10-C	3	11	3-11-A

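### SAP section 6.2: with i meaning condition, as stated, the printed rules for X_li and T_3l contradict their own prose; T_3l is never 1 and X_li takes in sequence 1's continued-exposure period

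*SAP*

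**What the plan says.** All of this is in the SAP.

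- **Meaning of i.** Section 6.2 introduces the outcome with "i = 0 or 1 (0 = control condition, 1 = intervention condition").
- **Condition by period.** Figure 1 in section 3.1 gives the sequence codes 011 and 001, with the key "0=control condition; 1=intervention condition". Both codes end in 1. Section 6.2 agrees for sequence 1: "The classes in the sequence 1 underwent continued effects of receiving the classroom sensitization intervention (intervention condition) in the third time period". Appendix 1 agrees for the other group: "Sequence 2 Group B: 36-70 classes to receive the intervention condition in the third time period".
- **Rule for X_li.** It is 1 if i = 1 and l = 2, glossed as sequence 1, "or if i = 1 and l = 3 (sequence 2 classes that received classroom intervention at period 3").
- **Rule for T_2l.** "equals 1 if i = 0 and l = 2", glossed as sequence 2 still under control.
- **Rule for T_3l.** It marks the third period, where "classes of sequence 1 experienced continued effects of the classroom sensitization intervention (equals 1 if i = 0 and l = 3").
- **Coefficients.** In prose, theta_1 belongs to sequence 1 in period 2 and sequence 2 in period 3, and is named as the main parameter. Theta_2 belongs to sequence 2 in period 2, and theta_3 to sequence 1 in period 3.
- **Stata call.** It uses t2, effect_lag0 and effect_lag1. The text describes what each stands for but does not state a rule by sequence and period.

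**The concern.** Within single sentences, the algebra and the gloss pick out different classes. With i as defined, the rule for T_3l asks for classes in the control condition in period 3, and there are none. The rule for X_li in period 3 asks for classes in the intervention condition, which is all 70, while the bracket limits it to sequence 2.

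The primary parameter is at stake. Theta_1 is meant to be the immediate effect of the classroom session, kept apart from what happens in the next four weeks. A programmer who codes from the algebra merges those two, and the separate continued-effect term disappears. A programmer who codes from the prose gets the intended model. Each could claim to follow the prespecified analysis, and their estimates differ unless the immediate and continued referral rates are equal. The secondary and exploratory models in section 6.3 refer back to section 6.2 and inherit the ambiguity.

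**Working it through.** The SAP attaches no figure to these indicators. The 92% power in section 3.6 rests on a within-period comparison and does not use them, so there is no plan figure to reproduce here.

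**Step 1: apply the rules to the six sequence-by-period cells.** The condition comes from Figure 1. The printed columns take i as condition; the intended columns follow the prose for theta_1 to theta_3.

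| Sequence, period | i | X printed | T2 printed | T3 printed | X intended | T2 intended | T3 intended |
|---|---|---|---|---|---|---|---|
| 1, 1 | 0 | 0 | 0 | 0 | 0 | 0 | 0 |
| 1, 2 | 1 | 1 | 0 | 0 | 1 | 0 | 0 |
| 1, 3 | 1 | **1** | 0 | **0** | **0** | 0 | **1** |
| 2, 1 | 0 | 0 | 0 | 0 | 0 | 0 | 0 |
| 2, 2 | 0 | 0 | 1 | 0 | 0 | 1 | 0 |
| 2, 3 | 1 | 1 | 0 | 0 | 1 | 0 | 0 |

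The two codings differ in one cell, sequence 1 in period 3. T_2l is right as printed. With the constant included, the printed coding gives a design matrix of rank 3 for four parameters, so theta_3 is not estimable. The intended coding has rank 4.

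**Step 2: try other meanings of i.**

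- i = 1 for sequence 1: X covers sequence 1 in periods 2 and 3, and T3 falls on sequence 2 in period 3. This does not match the prose.
- i = 1 for sequence 2: X covers sequence 2 in periods 2 and 3, T2 falls on sequence 1 in period 2, and T3 on sequence 1 in period 3. This does not match either.
- i = 1 only in the period when the session is introduced: all the rules match their brackets and Figure 3. This is not the meaning that section 6.2 gives to i.

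**Step 3: size of the shift in theta_1 if the printed rules were coded.**

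Inputs from section 3.6: 5% referral under control, 15% under intervention, 70 classes averaging 50 students. With 35 classes per sequence, the cells are taken as equal in size. Assumptions: 5% applies to period 1 (the reference in both codings), 15% is the immediate rate, and c is the referral rate in sequence 1, period 3. The SAP gives no value for c.

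Under an independence working correlation, the estimate of theta_1 is the log odds ratio of the pooled proportion in the cells with X = 1 against period 1.

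- Intended coding: OR = (0.15/0.85) / (0.05/0.95) = 0.1765 / 0.0526 = 3.35, whatever c is.
- Printed coding: pooled rate p = (15% + 15% + c) / 3, and OR = [p/(1 - p)] / 0.0526.

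| c (assumed) | p | OR, printed rules | OR, intended |
|---|---|---|---|
| 15% | 15.0% | 3.35 | 3.35 |
| 10% | 13.3% | 2.92 | 3.35 |
| 5% | 11.7% | 2.51 | 3.35 |
| 2% | 10.7% | 2.27 | 3.35 |

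**Step 4: a half repair.** Suppose T3 is corrected to sequence 1, period 3, but the printed X is kept. The model then has full rank and theta_1 is again as intended. Theta_3, however, now compares continued with immediate exposure. At c = 10% its OR is (0.10/0.90) / (0.15/0.85) = 0.63, against (0.10/0.90) / (0.05/0.95) = 2.11 for the comparison with period 1. The two rules have to be corrected together.

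**The case against.** The best defence is that the SAP leaves little doubt about what is meant. The prose for the thetas, the list of effects in section 6.2, Figure 3 and the brackets inside the disputed rules all name the same cells. The Stata variables separate immediate from continued exposure, and the data set holds each class's sequence and the period of its session (section 4.1). An indicator that is 0 on every record would be hard to miss. The period 2 analysis in section 6.4 does not use these indicators at all.

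This stands, and it rules out some stronger readings. A reader might infer that no single meaning of i can make the rules agree with Figure 3. That is not so: reading i as marking the period in which the session is introduced reconciles them, and section 6.2 itself describes X_li in terms of introduction. A reader might also infer that the formulas are the only formal definition of the coding. They are not, because the coefficients are assigned to explicit sequence-by-period cells.

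What does not stand is the conclusion that nothing needs correcting. The introduction reading conflicts with the stated definition of i, and it would label sequence 1 in period 3 as control when Figure 3 and the accompanying list place it in the intervention condition. The printed rules remain wrong under the meaning that the SAP gives.

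**Conclusion.** The point holds as a contradiction between formula and prose in the primary model. With i as condition, T_3l is never 1, theta_3 is not estimable, and X_li includes sequence 1's second exposed period. These facts need no assumption beyond Figure 1 and the definition of i.

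A reader might go further and say that the main effect does absorb the continued-exposure cell. The SAP does not support that as a fact about the planned analysis. It would happen only if the data were coded from the printed formulas against the stated intent.

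In that case the size depends on a rate that the SAP does not give. Over assumed continued rates from 15% down to 2%, the odds ratio for theta_1 would run from 3.35 (no change) to 2.27. It would rise above 3.35 if the continued rate exceeded the immediate one. These values also assume equal cells and the section 3.6 planning rates.

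The correction should be made, because a plan for the primary outcome should permit only one coding. The intended model itself is not in question here.

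**What to change.** In section 6.2, replace the rules that use i by rules in sequence s (1 or 2) and period l, and name the Stata variable for each:

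- X = effect_lag0 = 1 if (s = 1 and l = 2) or (s = 2 and l = 3), otherwise 0.
- T2 = t2 = 1 if s = 2 and l = 2, otherwise 0. This is the same cell as now.
- T3 = effect_lag1 = 1 if s = 1 and l = 3, otherwise 0.

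Correct X and T3 together. State in section 6.3 that the models referring back to section 6.2 use the same coding. If i is kept in the outcome notation, let it mean condition only and leave it out of these rules.

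The cost is a few lines of SAP text. Data collection, randomisation, conduct and the Stata command do not change.
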